#### **9.4. Background and Demographic Characteristics**

Demographic and baseline disease characteristics will be summarized by study phase and by cohort/treatment group within the Phase 1b and Phase 2 segments. Age, height, body weight, and other continuous baseline characteristics will be summarized using descriptive statistics (N, mean, SDev, median, minimum, maximum), while age group, gender, race and other categorical variables will be summarized using frequency tabulations (count, percentage).

#### **9.5. Subject Disposition**

Subject disposition (analysis population allocation, subjects who entered, discontinued treatment/study, along with primary reason for discontinuation) will be summarized using frequency and percentage for study phase/follow-up periods and by cohort/treatment arm. A summary of enrolled subjects by study phase, by site, and by country will be provided as well. Protocol deviations/violations will be summarized using frequency tabulations. Supportive corresponding subject listings will also be provided.

#### **9.6. Efficacy Analysis**

##### **9.6.1. Phase 1b**

Response to treatment will be confirmed internally using modified IWG.

Subjects who discontinue study treatment to receive HSCT will remain on study and will be followed until documented disease progression or end of trial.

Point estimates and 95% confidence intervals for response rates will be summarized for each dose level and overall. Response will be summarized as investigator-assessed overall response rate (ORR), which includes responses of CR, CRp, CRi, morphologic leukemia-free state (MLFS), and PR. Other measures of clinical activity, including duration of remission, duration of response, EFS, Sponsor-assessed CR/ CRh (based on laboratory dataset), overall survival, and time to remission/response may be summarized as appropriate. All time to event endpoints will be estimated using Kaplan-Meier methods. Point estimates and 95% confidence intervals will be provided where appropriate.

##### **9.6.2. Phase 2 AG-221 Randomized Stage**

For subjects in Phase 2, response will be primarily assessed by investigator review.

All efficacy analysis will be performed in the ITT population. Key efficacy analysis will also be performed on the mITT and EAP as supportive evidence and to assess the robustness of the efficacy findings. Subjects will be analyzed according to randomized treatment group.

The primary efficacy endpoint ORR is defined as the rate of responses including CR, CRi, CRp, MLFS and PR that are assessed by investigator according to modified IWG AML response criteria. The ORR will be summarized by treatment group. The treatment difference in ORR will be tested using the Chi squared test at a two-side 0.2 level and in the ITT population. This test will provide the pivotal p-value for the comparison of the ORR of the oral AG-221 + SC azacitidine versus azacitidine mono therapy. Estimated response rate with 80% and 95% confidence intervals will also be provided.

**Event-free survival (EFS)** is defined as the interval from the date of randomization to the date of documented morphologic relapse, progression, or death from any cause, whichever occurs first. The analysis of the **EFS** will be conducted using the log-rank test in the ITT population. This test will be used for the comparison of the two EFS curves of oral AG-221+ SC azacitidine versus azacitidine mono therapy. The Cox proportional hazards regression model will be used to estimate the hazard ratio and a 95% confidence interval for the hazard ratio.

**Duration of response** is defined as time from the first documented CR/CRi/CRp/MLFS/PR to the date of the first documented morphologic relapse, progression according to modified IWG AML response criteria ([Appendix F](#)), or death due to any cause, whichever occurs first. Subjects without morphologic relapse, progression, or death due to any cause will be censored at the date of the last response assessment. Duration of response will be assessed using Kaplan-Meier methods. Point estimates and 95% CIs will be provided where appropriate for the median and other quantiles.

**Time to response** is defined as time from the date of first dose to the date of first occurrence of response, which includes CR, CRi, CRp, PR and MLFS as determined by investigator. Time to response will be summarized using descriptive statistics in subjects with documented CR, CRi, CRp, PR and MLFS as determined by the investigator.

For **HRQoL** data, analyses will address the mean differences by treatment group on the EORTC QLQ-C30 scale and subscale scores and the treatment group differences in the proportion of subjects who achieve minimal clinically important differences. EQ-5D-5L will be scored according to the instrument guidance and analyzed accordingly.

Overall survival and one year survival rates will be analyzed using Kaplan-Meier method, and the treatment comparison will be conducted using log-rank test.

The other secondary endpoints include complete remission rate, best overall objective response rate, rate of hematologic improvement (HI), the sponsor assessed CR/CRh (based on laboratory dataset) and duration of CR/CRh. These endpoints will be analyzed using the statistical methods mentioned above or other statistical methods as appropriate. As noted, CRh is not available from the investigator assessment. As a result, the analyses on CR/CRh will be based on the sponsor derived assessment.

## 9.7. Safety Analysis

All safety analyses will be performed on the safety population.

Adverse events will be summarized by Medical Dictionary for Regulatory Activities (MedDRA) system organ class and preferred term. Separate tabulations will be produced for all treatment-emergent AEs (TEAEs), treatment-related AEs (those considered by the investigator as at least possibly drug related), SAEs, discontinuations due to AEs, and AEs with at least a Grade 3 severity. By-subject listings will be provided for deaths, SAEs, DLTs, and AEs leading to discontinuation of treatment.

Clinical laboratory results will be listed and summarized descriptively by dose group, which will also include a display of change from baseline. Laboratory values outside of the normal ranges will be identified. Clinically significant laboratory abnormalities that meet Grade 3 or Grade 4 criteria according to the CTCAE version 4.03 will be listed and summarized. Graphical displays of select laboratory parameters over the course of the study may be provided where useful to assist in the interpretation of results.

Descriptive statistics will be provided for ECG intervals and vital sign measurements presented as both actual values and changes from baseline to the post-baseline visit and to the last visit in the study. Electrocardiograms will also be analyzed for QTc intervals, QTc > 480 and > 500, and increase > 30 and > 60 msec.

Tolerability of the study drug will be assessed by summarizing the number of dose interruptions and dose reductions. Reasons for dose interruption and dose reductions will be listed by subject and summarized.

Subjects in Phase 1b with the same dose level may be pooled with those in Phase 2 for safety presentation as appropriate.

## 9.8. Interim Analysis

There is no formal interim analysis based on the pre-specified statistical stopping rule and type 1 error rate adjustment. However, the DMC will review data periodically in order to monitor the drug toxicity and treatment inferiority/superiority.

## 9.9. Other Topics

### 9.9.1. Data Monitoring Committee

An external DMC will be convened that will include medical hematologists/oncologists with experience in treating subjects with AML and a statistician, all of whom are not otherwise involved in the study conduct. During the course of the study, the DMC will review the safety data on a regular basis. Reports of aggregate data summaries and individual subject data listings, as appropriate, will be prepared for the DMC members for each scheduled meeting. Operational details for the DMC will be detailed in the DMC charter.

[figure not shown]
For efficacy data, the DMC will initially review ORR, DOR, EFS and OS after at least 10 subjects have been enrolled in azacitidine mono therapy arm. The DMC will review efficacy data again after each additional 10 subjects per azacitidine mono therapy arm has been enrolled. The

[figure not shown]
DMC will also review the safety data periodically and make recommendations at the end of each review based on observed safety and treatment inferiority/superiority.

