2. INTRODUCTION

This statistical analysis plan (SAP) describes the analyses and data presentations for Celgene's protocol AG-221-AML-005 "A PHASE 1B/2 OPEN-LABEL, RANDOMIZED STUDY OF 2 COMBINATIONS OF ISOCITRATE DEHYDROGENASE (IDH) MUTANT TARGETED THERAPIES PLUS AZACITIDINE: ORAL AG-120 PLUS SUBCUTANEOUS AZACITIDINE AND ORAL AG-221 PLUS SC AZACITIDINE IN SUBJECTS WITH NEWLY DIAGNOSED ACUTE MYELOID LEUKEMIA HARBORING AN IDH1 OR AN IDH2 MUTATION, RESPECTIVELY, WHO ARE NOT CANDIDATES TO RECEIVE INTENSIVE INDUCTION CHEMOTHERAPY" which was issued on 29Sep2015 and amended on 04Feb2016 and 25Oct2016. It contains definitions of analysis populations, derived key efficacy variables, and statistical methods for the analysis of efficacy and safety data.

Throughout this SAP, the treatment arms will be referred to as AG-120 500 mg + AZA 75 mg/m² in Dose-finding, AG-120 500 mg + AZA in Expansion, AG-221 100 mg + AZA 75 mg/m², and AG-221 200 mg + AZA 75 mg/m² during Phase 1b dose-finding and AG-120 expansion stage; the treatment arms will be referred to as AG-221 100 mg + AZA 75 mg/m² and AZA alone during Phase 2 randomized stage. Treatment arms AG-120 + AZA 75 mg/m² in Dose-finding and AG-120 + AZA in Expansion refer to the combination of AG-120 Orally (PO) plus azacitidine (AZA) subcutaneously (SC). Treatment arm AG-221 + AZA refers to the combination of AG-221 PO plus azacitidine SC. Treatment arm AZA alone refers to azacitidine SC alone.

This SAP provides a comprehensive and detailed description of the strategy, rationale, and statistical techniques to evaluate the efficacy and safety endpoints. The purpose of the SAP is to ensure the credibility of the study findings by pre-specifying the statistical approaches to the analysis of study data prior to database lock for final analysis. There is one formal interim analysis but no pre-specified statistical stopping rule and type 1 error rate adjustment. However, the DMC will review data periodically in order to monitor the drug toxicity and treatment inferiority/superiority. There will be several interim looks throughout the trial. The SAP may be amended as necessary to accommodate a protocol amendment and will be finalized and signed off prior to the clinical database lock for the primary and final analysis. All statistical analyses detailed in this SAP will be conducted using SAS[®] Version 9.4.

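### Do the DMC's repeated efficacy reviews undermine the two-sided 0.2 and 75% power stated for the final ORR test?

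*Protocol*

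**What the plan says.** Protocol 9.9.1 sets the schedule: "the DMC will initially review ORR, DOR, EFS and OS after at least 10 subjects have been enrolled in azacitidine mono therapy arm", and then "The DMC will review efficacy data again after each additional 10 subjects per azacitidine mono therapy arm has been enrolled". After each review the DMC is to "make recommendations at the end of each review based on observed safety and treatment inferiority/superiority". With 33 control subjects and 2:1 allocation, that means looks at about 10, 20 and 30 controls, or roughly 30, 60 and 90 of 99 subjects.

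Protocol 9.8 says: "There is no formal interim analysis based on the pre-specified statistical stopping rule and type 1 error rate adjustment". It adds that "the DMC will review data periodically in order to monitor the drug toxicity and treatment inferiority/superiority". SAP 2 says: "There is one formal interim analysis but no pre-specified statistical stopping rule and type 1 error rate adjustment", and also "There will be several interim looks throughout the trial".

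The confirmatory step is a single one (protocol 9.6.2): "The treatment difference in ORR will be tested using the Chi squared test at a two-side 0.2 level and in the ITT population". Protocol 9.3 gives 75% power for 50% against 30% with 66 and 33 subjects at two-sided 0.2.

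Protocol 3.1.2.5 leaves the DMC's responsibilities, authorities and procedures to a prospective charter, and 9.9.1 leaves operational details to the same charter. Protocol 3.1.2.5 and the DMC paragraph that follows SAP section 13 mention safety review and do not mention efficacy.

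**The concern.** A committee that sees four efficacy endpoints three times during accrual, and may speak to superiority, looks like a group sequential design without boundaries. If a favourable look could end the trial or support a claim, the error rate behind the final p-value would exceed 0.2. The ORR difference at such a stop would also be overstated. Because the results are meant to inform a Phase 3 trial, an inflated estimate would carry forward.

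Three features of the text strengthen the impression:

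- No supplied passage says what a superiority recommendation can or cannot lead to.
- The sponsor's right to terminate in protocol 13.8 is open-ended.
- Protocol 9.8 and SAP 2 appear to disagree on whether a formal interim analysis exists at all.

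**Working it through.** **Inputs.** ORR 30% and 50%, 33 and 66 subjects, two-sided 0.2 (protocol 9.3); uncorrected chi-squared test (9.6.2); looks at 10, 20 and 30 controls (9.9.1), with the final test at 33.

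**Stated power.** With z = 1.2816 for two-sided 0.2:

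- Pooled rate = (66×0.50 + 33×0.30)/99 = 0.4333. Null SE = √[0.4333×0.5667×(1/33 + 1/66)] = 0.1056.
- SE under the alternative = √(0.21/33 + 0.25/66) = 0.1008.
- Power = Φ[(0.20 − 1.2816×0.1056)/0.1008] = Φ(0.641) = 73.9%. With the unpooled SE throughout, Φ(0.20/0.1008 − 1.2816) = Φ(0.703) = 75.9%.
- Exact enumeration over all responder counts, rejecting when |Z| > 1.2816, gives 75.3%.

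The stated 75% is therefore the power of one final test.

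**Stated error, one final test.** The exact two-sided error at a common ORR of 30/35/40% is 0.2032/0.2081/0.2145. The superiority side is 0.1015/0.1036/0.1068.

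**If a look could support a claim.** This is an exact recursion over responder counts in both arms. Case A assumes every enrolled subject is evaluable at each look (10/20/30 controls). Case B assumes response lag, with 5/15/25 controls evaluable. Both sets of evaluable counts are assumptions, because the documents give no accrual rate. Ranges run over a common ORR of 30% to 40%.

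| Interim bar (two-sided p) | Two-sided error, A | Two-sided error, B | Superiority side |
|---|---|---|---|
| none (plan as written) | 0.203-0.215 | 0.203-0.215 | 0.102-0.107 |
| 0.001 | 0.203-0.215 | 0.204-0.215 | essentially unchanged |
| 0.01 | 0.207-0.219 | 0.210-0.221 | not tabulated |
| 0.05 | 0.235-0.247 | 0.256-0.262 | A 0.115-0.122, B 0.117-0.126 |
| 0.2 at every look | 0.418-0.435 | 0.483-0.491 | 0.21-0.22 in A |

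At the 0.001 bar power stays at 75.3%. An O'Brien-Fleming type boundary at the case A looks holds error at about 0.20 with power 74.5%. No passage proposes claims at 0.2 at every look.

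**If a look could lead only to an inferiority stop.** The false-superiority rate does not rise. Power becomes 75.1% (A) or 74.3% (B) if the bar is p<0.2 in the wrong direction. It becomes 70.8% (A) or 65.4% (B) if accrual stops whenever the combination trails.

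**Overstatement at an early stop.** In case A with a true difference of 20 points, a first superiority crossing at p<0.05 shows on average 47, 32 and 26 points at the three looks.

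**The two interim statements side by side.** Protocol 9.8 denies a formal interim analysis based on a stopping rule and alpha adjustment. SAP 2 names one formal interim and says that it too has no rule and no adjustment. Both have the DMC monitoring inferiority and superiority. They differ on whether to call a look formal. They agree on the two facts that determine the error rate.

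**The case for a change.** The strongest opposing case is that silence is not a prohibition. Neither supplied document says that a superiority finding cannot end the trial. Under the design rates, a look judged at p<0.05 would cross early in 51% of trials in case A, so the route is not remote. A charter cannot make protocol 9.8 and SAP 2 read alike. One consistent sentence would cost no subjects and no power, and a record of the looks made would let a reader confirm that the p-value can be taken at 0.2.

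Part of this stands. The wording differs, and a reader of these two documents alone cannot tell what a recommendation could trigger.

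The rest does not carry a change:

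- The consequences of a DMC recommendation are charter content. Protocol 3.1.2.5 says so, and the charter was not supplied. The supplied SAP text also runs from section 13 directly to section 17, so a fuller description of the interim may exist.
- A ban on superiority action is not needed to protect the stated figures. A strict bar such as p<0.001 leaves both intact, so choosing between a ban and a boundary is a trade-off.
- A ban on superiority action alone would not secure the 75% either, because undefined inferiority stops are what could lower power.
- The safety-only passages do not say that the DMC sees nothing else. SAP 2 and protocol 9.9.1 both disclose efficacy monitoring.
- The amendment justification reports that the primary-analysis CSR, with a 19 Aug 2019 cutoff, is finalized. New text could not pre-specify anything, and a list of looks made belongs in a study report.

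**Conclusion.** No change to the plan follows. With no stopping rule and one final ORR test, the stated two-sided 0.2 and 75% power are delivered: exact error 0.203-0.215 and power 75.3%. The gap about consequences is detail that the protocol assigns to the DMC charter. The formal-interim discrepancy is a wording slip that alters no analysis.

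A material effect would need a loose superiority bar or an aggressive inferiority stop. Claims at p<0.05 would put two-sided error at 0.235-0.262, with the superiority side up by about 1.4 to 1.9 points (0.1015 to 0.1151 at the low end, 0.1068 to 0.1256 at the high end). Stopping whenever the combination trails would put power at 65-71%. No passage sets either bar, and none reports a superiority action.

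This rests on the uncorrected chi-squared test, on ORR alone being modelled, on the assumed evaluable counts in cases A and B, and on the charter not providing a loose efficacy stop.

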**9.9.2. Steering Committee**

The conduct of this trial will be overseen by a steering committee, presided over by the coordinating principal investigator and if possible the representative Regional Investigators from countries participating in this study. The steering committee will serve in an advisory capacity to the sponsor. Operational details for the steering committee will be detailed in a separate steering committee charter.

Note: The steering committee is separate from the DMC.

## 10. ADVERSE EVENTS

### 10.1. Monitoring, Recording and Reporting of Adverse Events

An AE is any noxious, unintended, or untoward medical occurrence that may appear or worsen in a subject during the course of a study. It may be a new intercurrent illness, a worsening concomitant illness, an injury, or any concomitant impairment of the subject's health, including laboratory test values (as specified by the criteria in Section 10.3), regardless of etiology. Any worsening (ie, any clinically significant adverse change in the frequency or intensity of a pre-existing condition) should be considered an AE. A diagnosis or syndrome should be recorded on the AE page of the CRF rather than the individual signs or symptoms of the diagnosis or syndrome.

Abuse, withdrawal, sensitivity or toxicity to any investigational products should be reported as an AE. Overdose, accidental or intentional, whether or not it is associated with an AE should be reported on the overdose CRF. (See Section 7.2 for the definition of overdose.) Any sequela of an accidental or intentional overdose of any investigational products should be reported as an AE on the AE CRF. If the sequela of an overdose is an SAE, then the sequela must be reported on an SAE report form and on the AE CRF. The overdose resulting in the SAE should be identified as the cause of the event on the SAE report form and CRF but should not be reported as an SAE itself.

In the event of overdose, the subject should be monitored as appropriate and should receive supportive measures as necessary. There is no known specific antidote for AG-221, AG-120, or azacitidine overdose. Actual treatment should depend on the severity of the clinical situation and the judgment and experience of the treating physician.

All subjects will be monitored for AEs during the study. Assessments may include monitoring of any or all of the following parameters: the subject's clinical symptoms, laboratory, pathological, radiological or surgical findings, physical examination findings, or findings from other tests and/or procedures.

All AEs will be recorded by the investigator from the time the subject signs informed consent until 28 days after the last dose of study treatment as well as those SAEs made known to the investigator at any time thereafter that are suspected of being related to any of the drugs in study treatment. AEs and SAEs will be recorded on the AE page of the CRF and in the subject's source documents. Refer to Section 10.5 for instructions on how to report SAEs to Drug Safety.

All AEs (SAEs and non-serious AEs) associated with confirmed or suspected SARS-CoV-2 infection must be collected from the date of the participant's written consent until 100 days following discontinuation of study drug. After the initial AE/SAE report, the investigator is required to proactively follow each participant at subsequent visits/contacts. All AEs (SAEs and non-serious AEs) associated with confirmed or suspected SARS-CoV-2 infection will be followed until resolution, the condition stabilizes, the event is otherwise explained, the event is deemed irreversible, the participant is lost to follow-up or for suspected cases, until SARS-CoV-2 infection is ruled out.

### 10.2. Evaluation of Adverse Events

A qualified investigator will evaluate all adverse events as to:

### 10.2.1. Seriousness

An SAE is any AE occurring at any dose that:

- Results in death;
- Is life-threatening (ie, in the opinion of the investigator, the subject is at immediate risk of death from the AE);
- Requires inpatient hospitalization or prolongation of existing hospitalization (hospitalization is defined as an inpatient admission, regardless of length of stay);
- Results in persistent or significant disability/incapacity (a substantial disruption of the subject's ability to conduct normal life functions);
- Is a congenital anomaly/birth defect;
- Constitutes an important medical event.

Important medical events are defined as those occurrences that may not be immediately life-threatening or result in death, hospitalization, or disability, but may jeopardize the subject or require medical or surgical intervention to prevent one of the other outcomes listed above. Medical and scientific judgment should be exercised in deciding whether such an AE should be considered serious.

Events **not considered** to be SAEs are hospitalizations for:

- a standard procedure for protocol therapy administration. However, hospitalization or prolonged hospitalization for a complication of therapy administration will be reported as an SAE.
- routine treatment or monitoring of the studied indication not associated with any deterioration in condition.
- the administration of blood or platelet transfusion as routine treatment of studied indication. However, hospitalization or prolonged hospitalization for a complication of such transfusion remains a reportable SAE.
- a procedure for protocol/disease-related investigations (eg, surgery, scans, endoscopy, sampling for laboratory tests, bone marrow sampling). However, hospitalization or prolonged hospitalization for a complication of such procedures remains a reportable SAE.
- hospitalization or prolongation of hospitalization for technical, practical, or social reasons, in absence of an AE.
- a procedure that is planned (ie, planned prior to start of treatment on study); must be documented in the source document and the CRF. Hospitalization or prolonged hospitalization for a complication remains a reportable SAE.
- an elective treatment of or an elective procedure for a pre-existing condition, unrelated to the studied indication, that has not worsened from baseline.
- emergency outpatient treatment or observation that does not result in admission, unless fulfilling other seriousness criteria above.

If an AE is considered serious, both the AE page/screen of the CRF and the SAE Report Form must be completed.

For each SAE, the investigator will provide information on severity, start and stop dates, relationship to the IP, action taken regarding the IP, and outcome for each individual drug in study treatment.

